# End of Stage 2/End of Study (Month 48)

At the Month 48/ end of study (EOS) visit Stage 2, the subject and their parent/guardian will return to the study site with their randomized study medication for an evaluation of treatment adherence. The modified ATI will be completed by the parent/guardian and subject prior to the Investigator's examination of the subject. The parent/guardian QoL questionnaire should be completed prior to the subject's questionnaire. Study staff will verify completion of the QoL questionnaires by both the parent/guardian and the subject.

Once the modified ATI is completed, subjects will undergo a measurement of height, weight, HR, BCVA measurement (distance and near), photopic pupil size measurement, SLE, tonometry, dilated fundus examination, cycloplegic autorefraction, axial length, and, if possible, crystalline lens thickness. Sites will update concomitant medications, conduct AE assessment, review e-diary, and perform treatment adherence assessment. The site staff will uninstall the Medidata eCOA application (installed on the cell phone) or retrieve the device provisioned by Medidata and provided to the subject.

## **Early Termination Visits**

Every effort should be made to keep subjects in the study and conduct all study visits as scheduled. If a subject is discontinued from study medication before the Month 48 visit, then all Month 48 (EOS) procedures should be performed at the visit the subject is discontinued.

If a subject is off study medication and is being followed for safety assessments then an EOS Month 36 visit should be completed, as these subjects will not continue on to Stage 2.

#### Unscheduled visits

Unscheduled visits may occur at the Investigator's discretion to address any possible issues the subject may experience that are of concern to the subject or parent/guardian (e.g., blurry vision, pain, redness in one or both eyes).

#### **Efficacy Assessments:**

- SER error in each eye measured by cycloplegic autorefraction
- Axial length
- Crystalline lens thickness (exploratory efficacy measurement)

#### **Treatment Adherence:**

Treatment adherence will be measured by study medication accountability. Throughout treatment (efficacy/safety portion and randomized cross-over portion), the amount of unopened medication units will be recorded at each study visit.

#### **Documentation of Mode of Administration:**

At the EOS Month 36 and EOS Month 48, site will document mode of administration by asking the subject or their parent/guardian:

- Who administered the eyedrops to the subject during the study (i.e., self-administered or administered by parent/guardian)?
- Was there a transition in the dosing administrator?
- If yes, at what approximate age did the transition occur?

# **Safety Assessments:**

- Heart Rate
- Monocular BCVA in each eye at distance and near
- Photopic pupil size
- Slit Lamp Exam

- Dilated fundus examination
- Adverse Events
- Tonometry

#### **Data and Safety Monitoring Plan:**

To minimize risk and ensure the immediate safety of study subjects, both local and systemic anticholinergic and other potential effects of study medication will be measured at each visit. Parameters such as heart rate, mydriasis, photophobia, blurred near vision, ocular and conjunctival inflammation and allergic reactions to study medication will be carefully and routinely monitored to assess both safety and tolerability.

All safety data will be collected and entered in the eCRF allowing for real-time review. Medical review will be performed concurrently with Data Management's review of data and issue of queries to sites. The aim of the medical review is to monitor eligibility issues, assess potential protocol deviations and identify safety issues.

In addition, the peer-reviewed and grey literature as well as global databases of AEs from other atropine products will be routinely and continually monitored.

# Withdrawal of Subjects:

All subjects randomized into the study will be encouraged to complete all study assessments through the Month 48 Visit (End of Study), including subjects that cannot or do not wish to continue study treatment (withdraw consent/assent from study treatment but are willing to continue study visits).

The following are the criteria for considering withdrawal from the study (Study discontinuation prior to Visit Month 48):

- Withdrawal of subject consent/assent to continue with study visits.
- If the site and/or the overall study is terminated for any reason.
- The Investigator considers it is in the best interest for the subject to leave the study. This may include the development of damage to the cornea (Section 8.5 Discontinuation of Study Medication).

If a subject withdraws from the study, the reason for the subject's withdrawal will be recorded in the electronic case report form (eCRF).

If a subject is discontinued from study medication before the Month 48 visit, then all Month 48 procedures should be performed at the visit the subject discontinues study medication. The subject should continue in the study off study medication. Subjects should be encouraged to return for the 6 Month interval visits; however, returning for the 12 Month interval visits is essential. Subjects discontinuing study medication prior to Month 36 would continue to be seen for scheduled visits (at 6 Month or 12 Month intervals as noted above) until they reach the Month 36 interval.

#### **Criteria for Evaluation:**

#### Safety:

The safety of 0.01% and 0.02% Atropine Sulfate Ophthalmic Solution will be compared to Vehicle (placebo) with analysis of safety variables including ophthalmic safety assessments (BCVA, photopic pupil size, SLE, dilated fundus examination, and tonometry), HR, and AEs.

#### **Primary Efficacy Endpoint:**

The primary efficacy endpoint is the between-treatment group (Atropine Sulfate Ophthalmic Solution, 0.02% versus Vehicle) difference in the proportion of subjects who show < -0.50 D myopia progression (SER) at the Month 36 visit.

The primary and all secondary endpoints comprise a fixed sequence set of endpoints to be tested in order. A 2-sided significance level of 0.05 will be adopted.

# **Secondary Efficacy Endpoints:**

The secondary efficacy endpoints consist of:

- 1. Between-treatment group (Atropine Sulfate Ophthalmic Solution, 0.02% versus Vehicle) difference in the mean change from baseline in SER at the Month 36 visit.
- 2. Between-treatment group (Atropine Sulfate Ophthalmic Solution, 0.01% versus Vehicle) difference in the proportion of subjects who show < -0.50 D myopia progression (SER) from baseline at the Month 36 visit.
- 3. Between-treatment group (Atropine Sulfate Ophthalmic Solution, 0.01% versus Vehicle) difference in mean change from baseline in SER at the Month 36 visit.
- 4. Between-treatment group (Atropine Sulfate Ophthalmic Solution, 0.02% versus Vehicle) difference in the mean change from baseline in axial length at the Month 36 visit.
- 5. Between-treatment group (Atropine Sulfate Ophthalmic Solution, 0.01% versus Vehicle) difference in the mean change from baseline in axial length at the Month 36 visit.

#### **Statistical Methods:**

#### **Analysis Sets:**

Enrolled Set: All subjects enrolled.

Safety Set: All subjects who were administered at least one dose of study medication for a given stage.

Intent-to-treat (ITT) Set: All randomized subjects for a given stage.

Modified intent-to-treat (mITT) Set: All randomized subjects, for a given stage, aged 6 to 10 years at the time of randomization in Stage 1. This will be the population for the primary efficacy analyses.

Per Protocol Set (PPS): All subjects who remain in the study through end of stage and have no major or critical protocol violations (as defined in the SAP).

Modified Per Protocol Set (mPPS): All subjects in the PPS in each stage who were aged 6 to 10 years at the time of randomization in Stage 1.

#### **Statistical Analyses:**

The primary and secondary efficacy analyses will be performed using the mITT Set assuming data missing at random.

The primary analysis and any other analysis of binary response measures will be performed using a mixed-effects model based on the binomial distribution using a logit link function. The model will include subject, treatment group, visit, eye (left or right), and baseline age group (as randomized) and SER (as randomized) as independent variables and treatment group-by-visit interaction term included. Random intercepts for subject and eye within subject will be included using variance components and compound symmetry covariance structures, respectively. In addition, sensitivity analyses will be performed for the primary efficacy endpoint to assess the impact of missing data. These sensitivity analyses will be described in the statistical analysis plan.

For comparisons of mean change from baseline for continuous measures, the analysis will be performed using a mixed-effects model with a random intercept. The model will include treatment group, visit, eye (left or right), baseline age group (as randomized), and baseline SER group (as randomized) as independent variables and the treatment group-by-visit interaction. Will be included. The degrees of freedom will be determined using the Kenward-Roger approximation.

Random intercepts for subject and eye within subject will be included using unstructured covariance structures.

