#### **Sample Size:**

#### **Atropine Sulfate Ophthalmic Solution, 0.02%:**

A Fisher's exact test with a 0.05 two-sided significance level will have 95% power to detect the difference between an Atropine Sulfate Ophthalmic Solution, 0.02% responder proportion of 0.25 and a Vehicle responder proportion of 0.07 when the sample sizes are 136 and 91, respectively.

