# **Atropine Sulfate Ophthalmic Solution, 0.01%:**

A Fisher's exact test with a 0.05 two-sided significance level will have 90% power to detect the difference between an Atropine Sulfate Ophthalmic Solution, 0.01% responder proportion of 0.25 and a Vehicle responder proportion of 0.07 when the sample size in each group is 91.

**Table 2:** Schedule of Procedures

Assessment  Visit Number  Month	Screening Baseline a	Treatment Stage 1 (Office Visits Every 3 Months and Telephone Checks a ± 2 Weeks)															ll .	Treatment Stage 2 (Every 3 Months ± 2 Weeks)				
	1	T1	T2	3	Т3	3	T4	4	T5	5 12	6	7 18	8 21	9	10 27	11	12	13	14 39	15 42	16 45	17 48 (EOS) b
	0		2		4.5	6	7.5	9	10.5		15			24		30	33	3 36 (EOS) b				
Informed consent/assent c	X																					
Demographics/medical/ocular history	X																					
Prior/concomitant medication	X																					
Urine pregnancy test d	X																					
Re-consent/re-assent e																		X	X	X	X	X
Modified ATI questionnaires (QoL)																				Xef		Xef
Height and weight	X									X				X				X				X
Heart rate	X					X				X		X		X		X		X		X		X
Best-corrected visual acuity £g	X					X				X		X		X		X		X		X		X
Pupil size measurement (photopic)	X					Х				X		Х		X		X		X		X		X
Slit-lamp examination	X					X				X		X		X		X		X		X		X
Intraocular pressure	X					X				X		X		X		X		X		X		X
Dilated fundus examination	X									X				X				X				X
Cycloplegic autorefraction	X					X				X		X		X		X		X		X		X
Inclusion/exclusion criteria assessment	X																					
Randomization/re-randomization (M 36)	X																	X				
Axial length	X					Х				X		X		X		X		X		X		X
Crystalline lens thickness (where feasible)	X					Х				Х		X		X		Х		X		X		X
Collect study medication materials				X		X		Х		X	Х	X	X	X	X	X	Х	X	X	X	X	X

IND 130341

Assessment	Screening Baseline a		Treatment Stage 1  (Office Visits Every 3 Months and Telephone Checks a ± 2 Weeks)												Treatment Stage 2 (Every 3 Months ± 2 Weeks)							
Visit Number	1	T1	T2	2	Т3	3	T4	4	T5	5	6	7	8	9	10	11	12	13	14	15	16	17
Month	0	1	2	3	4.5	6	7.5	9	10.5	12	15	18	21	24	27	30	33	36	39	42	45	48
																		(EOS)b				(EOS)b
Concomitant medication review				Х		Х		Х		X	X	X	X	X	X	X	X	X	X	X	X	X
Adverse event assessment	X	X	X	X	X	X	X	X	X	X	X	X	X	X	X	X	X	X	X	X	X	X
Dispense study medication (frames/lenses) gh	Х			X		Х		X		X	X	X	X	X	X	X	X	X	X	X	X	

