The normalized SER will be used in all efficacy analyses for SER. SER values for randomization and stratification will not be normalized. Baseline SER will be normalized for use in the statistical analyses of efficacy. Both the original SER (from CRF) and normalized SER will be presented in listings. The astigmatism value for eligibility purpose will not be normalized because normalization to the corneal plane from a spectacle plane will always lead to a less minus power and hence will not change astigmatism eligibility for enrolled participants

This document is confidential.

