8.2.4. Between-treatment group (Atropine Sulfate Ophthalmic Solution, 0.02% versus Vehicle)  
Difference in the Mean Change from Baseline in Axial Length at Month 36

A secondary analysis will be performed on the between-treatment group (Atropine Sulfate Ophthalmic Solution, 0.02% versus vehicle) difference in the mean change from baseline in axial length at the Month 36 visit. The analysis method will be the same as the secondary efficacy analysis as described in 8.2.1 above.

Summary statistics will be presented along with a full data listing by treatment group.

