8.3.7. Between-treatment group (Atropine Sulfate Ophthalmic Solution, 0.02% versus Vehicle)  
Difference in the Time to Change from Baseline in Myopia Progression of -0.75 D SER

A tertiary analysis will be performed on the between-treatment group (Atropine Sulfate Ophthalmic Solution, 0.02% versus vehicle) difference in the time to change from baseline in myopia progression of -0.75 D SER.

The time to change in myopia progression of -0.75 D SER (days) = (first date with a change in myopia progression of -0.75 D or more – first date of treatment) +1. For subjects that were not observed to have a change in myopia progression of -0.75 D or more = Time to change in myopia progression of -0.75 D SER (days) [censored] = (Date of last known visit of Stage 1 – (first date of treatment) + 1.

The point estimate of the hazard ratios and the associated 95% confidence intervals will be obtained using the Cox proportional hazards regression model with fixed effects for treatment group, age at baseline, and baseline SER as covariates. An approximate Chi-square test based on Wald statistic will be used to compare treatment groups.

Summary statistics and associated survival curves (Kaplan-Meier estimates) will be presented along with a full data listing by treatment group.

Summary statistics will be presented along with a full data listing by treatment group.

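### As described, the confirmatory models adjust only for dichotomised age and SER; continuous baseline terms, above all axial length in the axial-length models, would give a small, nearly free efficiency gain

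*Protocol*

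**What the plan says.** The protocol synopsis (Statistical Analyses) gives the model for continuous endpoints as having treatment, visit, eye, treatment-by-visit and "baseline age group (as randomized), and baseline SER group (as randomized) as independent variables". Its binary model uses the same two baseline factors. SAP 8.1.1 repeats this for the primary endpoint, and its code places both factors in the CLASS statement.

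The strata are defined in SAP 6.6. Age is split at 9 years. SER is split at -3.00 D, and a subject counts as more myopic if either eye is beyond that value. SAP section 8 leaves the stratification SER un-normalised but says "Baseline SER will be normalized for use in the statistical analyses of efficacy".

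For axial length, SAP 8.2.4 states "The analysis method will be the same as the secondary efficacy analysis as described in 8.2.1 above", and 8.2.5 does likewise. The tertiary Cox model in SAP 8.3.7 instead names "fixed effects for treatment group, age at baseline, and baseline SER as covariates".

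The continuous values exist. Axial length and cycloplegic autorefraction are baseline procedures (protocol, Study Procedures). SAP 7.2 derives age from date of birth, and SAP 7.3 summarises baseline SER and axial length.

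SAP 8.2.1 to 8.2.3 appear in the SAP's table of contents but not in the supplied text. What follows about the mean-change models therefore rests on the protocol.

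**The concern.** A two-level factor carries less prognostic information than the measurement behind it. Three features make these strata coarse for this analysis:

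- The responder outcome is scored per eye, while the SER stratum is set per subject. An eye at -2.00 D whose fellow eye is at -3.25 D is labelled more myopic.
- The outcome SER is normalised because sites used different vertex distances. The stratum is not, so it keeps that inconsistency.
- The model is repeated in the ITT set, where one age level spans 9 to 17 years.

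For axial length, no baseline value of the measured quantity is described as a covariate. These are secondary endpoints 4 and 5, the last two steps of the fixed sequence, and the sample-size sections give power only for responder rates. At stake is some precision in the four mean-change tests and a little power in the two responder tests.

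**Working it through.** **Inputs from the documents.** "A 2-sided significance level of 0.05 will be adopted" (protocol, Primary Efficacy Endpoint). For 0.02% versus Vehicle: "A Fisher's exact test with a 0.05 two-sided significance level will have 95% power to detect the difference", with a "responder proportion of 0.25 and a Vehicle responder proportion of 0.07 when the sample sizes are 136 and 91, respectively". For 0.01% versus Vehicle the stated power is 90%, with a "responder proportion of 0.25 and a Vehicle responder proportion of 0.07 when the sample size in each group is 91".

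**The plan's own figure.** Exact enumeration of Fisher's test gives power 0.956 with 136 and 91 (stated 95%) and 0.901 with 91 and 91 (stated 90%). Both reproduce. The test is unadjusted, so these figures do not depend on the covariates.

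**Which tests are linear.** In the fixed sequence (SAP section 8), steps 2, 4, 5 and 6 are mean changes in SER or axial length. Steps 1 and 3 are logit responder tests.

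**Mean-change tests.** Let R² be the share of outcome variance that continuous baseline covariates explain, and r the share of R² that the cuts retain. The residual variance with continuous terms relative to strata is V = (1 − R²)/(1 − rR²). The SE falls by 1 − √V, which is worth 1/V − 1 more subjects.

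Neither input is in the documents. For r, age uniform over 6 to 11 years cut at 9 retains 0.72. SER cut at 3 D retains 0.64 (truncated normal, mean 2.4 D, SD 1.2 D) to 0.74 (uniform from 0.5 to 6 D). A range of 0.60 to 0.75 covers these.

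| R² (assumed) | r | V | SE reduction | Equivalent extra subjects |
|---|---|---|---|---|
| 0.05 | 0.75 | 0.95/0.9625 = 0.987 | 0.7% | 1.3% |
| 0.05 | 0.60 | 0.95/0.97 = 0.979 | 1.0% | 2.1% |
| 0.15 | 0.75 | 0.85/0.8875 = 0.958 | 2.1% | 4.4% |
| 0.15 | 0.60 | 0.85/0.91 = 0.934 | 3.4% | 7.1% |
| 0.30 | 0.75 | 0.70/0.775 = 0.903 | 5.0% | 11% |
| 0.30 | 0.60 | 0.70/0.82 = 0.854 | 7.6% | 17% |

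A simulation agrees in scale (one outcome per subject, one visit, 2,500 runs per setting). Replacing the strata with continuous age, SER and an independent axial-length term, at total R² of 0.13, 0.19 and 0.31, cut the SE by about 2.3%, 3.9% and 7.0%.

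**Responder tests.** The formula above does not apply to a logit model. Simulated power at the design rates, strata then continuous terms:

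| Total R² | 0.02% (136 vs 91) | 0.01% (91 vs 91) |
|---|---|---|
| 0.13 | 0.965 → 0.966 | 0.927 → 0.930 |
| 0.19 | 0.965 → 0.969 | 0.936 → 0.938 |
| 0.31 | 0.976 → 0.982 | 0.940 → 0.953 |

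The gains run from 0.1 to 1.3 percentage points. Monte Carlo error is about 0.3 to 0.5 points, so the smallest cannot be told from zero.

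A second simulation (136 vs 91, about 1,500 runs per setting) kept the strata and added continuous age and SER. At assumed R² of 0.05, 0.15 and 0.30 the SE of the log odds ratio was 1%, 3% and 6-7% larger. Power moved from 0.968 to 0.969, 0.969 to 0.967 and 0.969 to 0.975.

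**Limits.** Neither simulation fits the two-eye repeated-measures model, and the covariates in the first were independent. Axial length and SER are correlated in practice.

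**The case against.** The strongest case against is that nothing here is wrong. Adjusting for the stratification factors as randomised is sound practice, the comparison is unbiased, and the stated power reproduces. The plan may also have little to gain for SER. If 36-month change is normal with equal SD, rates of 0.25 and 0.07 imply a standardised difference of −0.674 + 1.476 = 0.80. Power for mean SER change then exceeds 0.999 in both comparisons without any adjustment.

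For axial length, the endpoint is a change, so the baseline has already been subtracted. A baseline term helps only so far as the slope of the follow-up value on baseline differs from 1, and the documents do not give that slope.

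All of this stands, and it limits the point to efficiency of modest and uncertain size. It does not remove the point: the measurements are in hand, the change costs almost nothing, and the axial-length tests have no stated power to fall back on.

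A reader might also infer a contradiction from the SAP's statement that baseline SER is normalised for efficacy analyses. That statement may refer only to deriving change, or to a term in the sections not supplied. The Cox model's wording does not say its covariates are continuous, and it concerns a tertiary endpoint. Neither passage shows that a planned covariate was dropped.

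**Conclusion.** The point holds as a missed efficiency. In the protocol's description, and in the SAP's primary model, baseline adjustment stops at two dichotomised strata. For the four mean-change tests, continuous terms would reduce the SE by roughly 0.7% to 7.6% over assumed R² of 0.05 to 0.30 and retention of 0.60 to 0.75. For the two responder tests the gain is about 0 to 1.5 percentage points of power at the design effect.

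Two stronger readings are tempting and are not supported:

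- That the standard errors of all six confirmatory tests are larger than they need be. In a logit model, prognostic covariates usually raise both the conditional log odds ratio and its SE. The extra-subject equivalents therefore apply only to the linear models.
- That baseline axial length appears in none of the SAP's models. SAP 8.2.1, to which the axial-length analyses refer, could not be read. The supported statement is that the protocol describes no such term for secondary endpoints 4 and 5. That is the strongest part of the point.

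**What to change.** First read SAP 8.2.1 to 8.2.3 to see whether continuous baseline terms are already there. If they are not, then before Stage 1 unmasking and with both strata kept as factors:

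- Axial-length change: add continuous baseline axial length (per eye) and continuous age. This is the priority.
- SER change: add continuous age and eye-level normalised baseline SER.
- Responders: add the same age and SER terms, or prespecify that model as a supportive analysis. Either way, state that the odds ratio is then conditional on more covariates and is not the same quantity as the one now planned.

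Age should be used untruncated, because SAP 7.2 truncates it to whole years for summaries. As main effects, the new terms leave the treatment and treatment-by-visit contrasts unchanged.

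The cost is SAP wording and two terms per model, with no new data. If Stage 1 has already been unmasked, report these models as supportive only.

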# Statistical Analyses (cont'd):

Note, there will be 8 groups with different treatment histories tor Year 4:

Treatment Stage	Possible Treatment Histories											
Stage 1 (Years 1-3)	Atropine 0.01%	Atropine 0.01%	Atropine 0.01%									
Stage 2 (Year 4)	Atropine 0.01%	Atropine 0.02%	Vehicle									
Stage 1 (Years 1-3)	Atropine 0.02%	Atropine 0.02%	Atropine 0.02%									
Stage 2 (Year 4)	Atropine 0.01%	Atropine 0.02%	Vehicle									
Stage 1 (Years 1-3)	Vehicle	Vehicle										
Stage 2 (Year 4)	Atropine 0.01%	Atropine 0.02%										

For all subjects who respond in the Atropine Sulfate Ophthalmic Solution treatment groups at the Month 36 visit, summary statistics for the change in SER from Stage 2 baseline (Month 36 visit) will be presented at the Month 42 and Month 48 visits for each treatment history where subjects receive the same dose of Atropine Sulfate Ophthalmic Solution, a lower dose of Atropine Sulfate Ophthalmic Solution, or Vehicle.

Summary statistics will be presented for compliance collected in diaries, the frequency of switching from dosing by parent/guardian to dosing by subject, and the modified Amblyopia Treatment Index by visit and treatment group in Year 4.

